8.2 Responsibility for Analyses / In-House Blinding

The statistical analysis of the data obtained from this study will be the responsibility of the designee/ Clinical Biostatistics department of the Sponsor.

Period 1 is conducted using an open-label design, i.e., subjects, investigators, and Sponsor personnel will be aware of subject treatment assignments after each subject is enrolled and treatment is assigned. Period 2 is conducted using a double-blind design under in-house blinding procedures. The official, final database for Period 2 will not be unblinded until medical/scientific review has been performed, protocol deviations have been identified, and data have been declared final and complete.

Results of both periods will be presented in the CSR.

The interactive voice response system (IVRS) will generate and implement the randomized allocation schedule(s) for study treatment assignment.

8.3 Hypotheses / Estimation

The hypothesis and objectives of the study are stated in Section 3.0.

8.4 Analysis Endpoints

Efficacy and safety endpoints to be evaluated are listed below, followed by the descriptions of the derivations of selected endpoints. Additional exploratory endpoints to characterize the clinical response after re-treatment for a “flare” during Period 2 (such as time to response and extent of response), as well as disease control during Period 2, will be fully described in the supplemental SAP.

The baseline value will be defined as the latest measurement collected prior to the first dose of golimumab in Period 1 (Visit 2).

8.4.1 Efficacy Endpoints

8.4.1.1 Primary Efficacy Endpoint

The primary efficacy endpoint for this trial is the proportion of subjects without a disease activity “flare” during up to 12 months in Period 2 (in subjects who attained inactive disease status after receiving open-label golimumab in Period 1).

A “flare” is defined as ASDAS at two consecutive visits that both show *either* absolute score ≥ 2.1 *or* post-withdrawal increase (i.e., change from Visit 23) of ≥ 1.1 .

8.4.1.2 Secondary Efficacy Endpoints

During Period 2:

- Proportion of subjects with a “flare” in the treatment-withdrawal group or the reduced-treatment group who then show a clinical response after re-treatment with open-label golimumab;
- Time to a first “flare”;
- Proportion of subjects achieving ASAS20 response;
- Proportion of subjects achieving ASAS40 response;
- Proportion of subjects achieving BASDAI50 response;
- Proportion of subjects achieving ASAS partial remission;
- Proportion of subjects achieving inactive disease status: ASDAS < 1.3 score.

8.4.1.3 Exploratory Endpoints

- Predictors of “flare” after withdrawal of GLM.
- Time to clinical response after re-treatment with golimumab for a “flare”;
- Extent of clinical response after re-treatment with golimumab for a “flare” (including at 12 weeks after re-treatment)
- Proportion of subjects with disease control (subjects without “flare” or who attain clinical response after re-treatment for a “flare”);
- Change from Baseline in components of the (composite) secondary endpoints:
 - BASDAI (0 to 10 NRS);
 - Total Back Pain (0 to 10 NRS);
 - Morning Stiffness (0 to 10 NRS);
 - BASFI (0 to 10 NRS);
 - Patient's Global Disease Assessment (0 to 10 NRS);
 - ASDAS;
 - CRP (mg/L).
- Global Assessment of Disease by Investigator

8.4.2 Safety Endpoints

An initial description of safety measures is provided in Section 4.2.3.2.

Serious infections, serious opportunistic infections, active tuberculosis, malignancies, and serious systemic hypersensitivity (including anaphylactic reaction) are prespecified as “Tier-1” events (for analysis of differences between treatments) in double-blind Period 2.

8.4.2.1 Events of Clinical Interest

The following serious and non-serious AEs are considered events of clinical interest (ECI) and monitored for this trial:

- Elevated AST or ALT lab value that is ≥ 3 x the upper limit of normal (ULN) and an elevated total bilirubin lab value that is ≥ 2 x ULN and, at the same time, an alkaline phosphatase lab value that < 2 x ULN, as determined by way of protocol-specified laboratory testing or unscheduled laboratory testing.
- Clinically significant opportunistic infections and TB
- Clinically significant hypersensitivity reactions

8.4.2.2 Other Safety Endpoints:

- Change from baseline for laboratory safety parameters and vital signs;
- Proportion of subjects with clinical AEs, laboratory AEs, and anti-GLM antibodies;
- Markedly abnormal (MA) laboratory values

8.4.2.3 PK and Immunogenicity Endpoints

- GLM concentrations (PK endpoints/analyses are described in a supplemental SAP)
- Antibody status (positive/negative) for antibodies to GLM

8.4.3 Derivations of Efficacy Endpoints

8.4.3.1 Bath Ankylosing Spondylitis Disease Activity Index

The BASDAI is defined as follows:

Subject self-assessment of 6 questions, on a NRS from 0 to 10:

Q1. Fatigue/tiredness

Q2. Neck, back, or hip (spinal) pain

Q3. Pain/swelling in joints other than neck, back, or hip

Q4. Tenderness

Q5. Level of morning stiffness

Q6. Duration of morning stiffness

$$BASDAI \text{ score} = 0.2 (Q1+Q2+Q3+Q4 + 0.5 [Q5+Q6])$$

- BASDAI50 is defined as at least 50% improvement from baseline in the BASDAI score.

8.4.3.2 Ankylosing Spondylitis Disease Activity Score

The ASDAS is a composite index to assess disease activity in axial spondyloarthropathies.

The ASDAS is defined by calculating the following formula:

$0.12 \times \text{Back Pain}$	+	$0.06 \times \text{Duration of Morning Stiffness}$	+	$0.11 \times \text{Patient Global}$	+	$0.07 \times \text{Peripheral Pain/Swelling}$	+	$0.58 \times \text{Ln}(\text{CRP}+1)$
1. Back pain – BASDAI question 2: "How would you describe the overall level of neck, back or hip pain you have had?"								
2. Duration of Morning Stiffness – BASDAI question 6: "How long does your morning stiffness last from the time you wake up?"								
3. Patient Global – Patient global disease assessment (PGD _N) "How active was your spondylitis on average during the last week?"								
4. Peripheral Pain/Swelling – BASDAI question 3: "How would you describe the overall level of pain/swelling in joints other than neck, back or hips you have had?"								
5. Ln(CRP+1): natural logarithm of the C-reactive protein (mg/L) + 1								

Back pain, duration of morning stiffness, patient global, and peripheral pain/swelling are all assessed on a NRS from 0 to 10 to calculate the ASDAS. When the CRP level is below the limit of detection (or when the CRP level is <2 mg/L), a value of 2 mg/L is used to calculate the ASDAS [8].

8.4.3.3 Assessment in SpondyloArthritis international Society-related Endpoints

- ASAS20: A 20% improvement in response on the Assessment in SpondyloArthritis international Society (ASAS) scale is defined as meeting both criteria:
 1. An improvement of $\geq 20\%$ from Baseline and an absolute improvement from Baseline of ≥ 1 score (0 to 10 NRS) in at least 3 of the following 4 domains:
 - a) Pain: Total Back Pain score
 - b) Morning Stiffness (average of questions 5 & 6 of the BASDAI concerning morning stiffness)
 - c) Function: Bath Ankylosing Spondylitis Functional Index (BASFI)
 - d) Patient Global Disease assessment (on Numeric scale) (PGD_N)
 2. Absence of deterioration from Baseline ($\geq 20\%$ and an absolute change of ≥ 1 score (0 to 10 NRS) in the potential remaining domain.
- ASAS40: An ASAS40 response is defined as meeting $\geq 40\%$ improvement (with absolute improvement of ≥ 2 score (0 to 10 NRS) in at least 3 of the 4 domains and no worsening at all in the potential remaining domain.
- ASAS Partial Remission: ASAS partial remission is defined as reaching ≤ 2 score (0 to 10 NRS) in all 4 ASAS domains.

8.4.3.4 Bath Ankylosing Spondylitis Functional Index

The BASFI is calculated as the mean of 10 NRSs (0 to 10 score). Eight of the scales relate to functional capacity of subjects, while the other 2 relate to a subject's ability to cope with everyday life. An increase along the scale indicates a worsening condition.

8.4.3.5 Morning Stiffness

Morning stiffness is defined as the mean of questions 5 and 6 of the BASDAI concerning morning stiffness.

8.4.3.6 Patient's Global Disease Assessment

The PGD_N is completed as follows:

Subjects make an overall assessment of disease activity over the past week on NRS from 0 to 10, with 0 being not active to 10 being extremely active.

8.4.3.7 Total Back Pain

The TBP is completed as follows:

Subjects assess their average total back pain over the past week on a NRS from 0 to 10, with 0 being no pain to 10 being extreme pain.

8.4.4 Derivations of Safety Endpoints

Levels of laboratory values that are considered to be markedly abnormal have been defined for each laboratory parameter in [Table 4](#).

Table 4 Markedly Abnormal Criteria for Laboratory Parameters

Hematology laboratory parameters	
Test	Criteria Value
Hemoglobin (g/dL)	Decrease > 2.0 and Value < 8.0
Hematocrit (%)	Value < 27
Total WBC ($\times 10^3/\mu\text{L}$)	Value < 2.0 or Value > 20.0
Eosinophils, absolute ($\times 10^3/\mu\text{L}$)	Percent increase ≥ 100 and Value > 0.8
Lymphocytes, absolute ($\times 10^3/\mu\text{L}$)	Percent decrease ≥ 33 and Value < 1.0
Neutrophils, absolute ($\times 10^3/\mu\text{L}$)	Percent decrease ≥ 33 and Value < 1.5
Platelets ($\times 10^3/\mu\text{L}$)	Percent decrease ≥ 50 and Value < 75
Clinical chemistry laboratory parameters	
Test	Criteria Value
Albumin (g/dL)	Decrease ≥ 1.0 and Value < 2.5
Alkaline phosphatase (IU/L)	Percent increase ≥ 100 and Value > 250
ALT (IU/L)	Percent increase ≥ 100 and Value > 150
AST (IU/L)	Percent increase ≥ 100 and Value > 150
BUN (mg/dL)	Percent increase ≥ 66 and Value > 40
Calcium (mg/dL)	(Increase ≥ 2.0 and Value > 11.5) or (Decrease ≥ 1.5 and Value < 7.5)
Chloride (mEq/L)	Value < 85 or Value > 120
Creatinine (mg/dL)	Percent increase ≥ 66 and Value > 2.5
Potassium (mEq/L)	(Increase ≥ 0.8 and Value > 5.5) or (Decrease ≥ 0.8 and Value < 3.0)
Sodium (mEq/L)	(Increase ≥ 10 and Value > 150) or (Decrease ≥ 5 and Value < 125)
Total Bilirubin (mg/dL)	Percent increase ≥ 100 and Value > 1.5
Total protein (g/dL)	Value < 4.5 or Value > 10.0

8.5 Analysis Populations

8.5.1 Efficacy Analysis Populations

Period 2: The Full Analyses Set (FAS) population consists of all randomized subjects who received at least one dose of post-randomization study treatment. The “flare” Full Analyses Set (“flare” FAS) population is defined as all FAS subjects in the Treatment Withdrawal (PBO) arm or in the GLM Q2Mdose interval arm who “flare” during Period 2.

Subjects will be included in the treatment group to which they are randomized for the analysis of efficacy data using the FAS population. Details on the approach to handling missing data are provided in Section 8.6 Statistical Methods.

8.5.2 Safety Analysis Populations

Period 1 safety data will be analyzed separately from Period-2 safety data.

Period 2: The ASaT population consists of all Period 2 randomized subjects who receive at least one dose of post-randomization study treatment.

At least one laboratory or vital sign measurement obtained subsequent to at least one dose of study treatment is required for inclusion in the analysis of each specific parameter. To assess change from baseline, a baseline measurement is also required.

Subjects will be included in the treatment group corresponding to the study treatment they actually received for the analysis of safety data using the ASaT population. For most subjects this will be the treatment group to which they are randomized. Subjects who take incorrect study treatment for the entire treatment period will be included in the treatment group corresponding to the study treatment actually received.

Details on the approach to handling missing data for safety analyses are provided in Section 8.6 Statistical Methods.

8.6 Statistical Methods

Statistical approaches for efficacy analyses are described in Section 8.6.1. Statistical approaches for safety analyses are described in 8.6.2. Ninety-five percent confidence intervals will be generated for response rates of various endpoints as detailed below. Efficacy results that will be deemed to be statistically significant after consideration of the Type I error control strategy are described in Section 8.8, Multiplicity. Unless otherwise stated, all statistical tests will be conducted at the $\alpha=0.05$ (2-sided) level.

8.6.1 Statistical Methods for Efficacy Analyses

This section describes the statistical methods that address the primary and secondary objectives. Methods related to exploratory objectives and related to analyses of data during Period 1 will be described in the supplemental SAP.

Efficacy data for continuous and categorical endpoints from Period 1 and Period 2 will be summarized separately. In Period 2, efficacy data will be summarized for each treatment comparison (GLM QM vs. withdrawal [PBO] and GLM Q2M vs. withdrawal [PBO]). In case of re-treatment following a “flare”, efficacy data will also be summarized for the time before re-treatment vs. the time after re-treatment.

The primary efficacy endpoint, the proportion of subjects without a “flare” (comparing between the PBO and GLM QM arms and between the PBO and GLM Q2M arms) will be analyzed using the stratified Miettinen and Nurminen (M&N) method [5], with stratification based on CRP level (>6.0 mg/L *or* ≤ 6.0 mg/L) and weighting scheme based on sample-size weights.

In addition, a comparison of GLM QM vs. GLM Q2M will be conducted as an exploratory analysis.

The exact binomial method of Clopper and Pearson [6] will be used to calculate a 95% CI on the proportion of subjects re-treated with golimumab after a “flare” who show a clinical response.

Missing data for the primary endpoint will be handled as follows:

- Discontinuations: Subjects who enroll in Period 2 but discontinue prior to a “flare” will be counted as having a “flare”.
- Missing components: If partial data are missing for the components of ASDAS (BASDAI questions 2, 3, 6, PGD_N, and CRP), then a multiple imputation (MI) procedure will be used to calculate the ASDAS. Details of the MI procedure will be provided in the sSAP.

Missing data for the secondary endpoint of proportion of subjects with a clinical response to re-treatment with GLM for a “flare” will be handled as follows:

- Discontinuations: Subjects who “flare” in Period-2 but do not undergo re-treatment or discontinue prior to re-attainment of inactive disease will be counted in the group having “flare” without clinical response to re-treatment.
- Missing components data will be handled similarly as for the primary endpoint.

Time to first “flare” and time to clinical response after a “flare” will be summarized using a Kaplan-Meier (K-M) analysis and a stratified log rank test. The time to first “flare” analysis will be conducted in the FAS. Day 1 for the K-M analysis will be the start date of Period 2. Subjects who do not “flare” will be censored at the time of study discontinuation; subjects who are lost-to-follow-up will be censored at the time of last data available. For the time to first “flare” analysis, missing component data will be imputed as specified for the primary endpoint. Summaries may include the pooled dose-reduction arms (Treatment Withdrawal [PBO] arm plus GLM Q2M arm) vs. GLM QM arm, as well as the 3 treatment arms separately.

The proportion of subjects with a clinical response to re-treatment with GLM for a “flare” and the time to clinical response after re-treatment with GLM for a “flare” analysis will be conducted in the “flare” FAS.

Other binary-response endpoints will be summarized by time point with 95% confidence intervals calculated using the exact binomial method of Clopper and Pearson (Period 1) and stratified M&N (Period 2). These summaries will be based on observed data; no missing data will be imputed.

Continuous endpoints will be summarized by time point using descriptive statistics. These summaries will be based on observed data; no missing data will be imputed.

[Table 5](#) summarizes the key efficacy analyses.

Table 5 Analysis Strategy for Efficacy Variables

Endpoint/Variable (Description, Time Point)	Primary vs. Supportive Approach	Statistical Method	Analysis Population	Missing Data Approach
Primary Objective				
Proportion of subjects without a disease activity “flare”, in subjects who attained inactive disease status in Period 2	Primary	Stratified M&N [‡]	FAS	Non-responder imputation for early discontinuations, MI [§] for missing components
Secondary Objectives				
Proportion of subjects with a clinical response to re-treatment with golimumab after a “flare” in Period 2	Primary	Clopper and Pearson	Flare FAS	Non-clinical response imputation for early discontinuations or “flare” without re-treatment, MI [§] for missing components
Time to first “flare” in Period 2	Primary	Kaplan-Meier	FAS	MI [§] for missing components
[‡] Miettinen and Nurminen. [§] MI=Multiple Imputation of ASDAS individual components used to determine Inactive Disease status.				

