At Month 10 (Visit 23; see also Trial Flow Chart – Section 6.1), evaluations are performed to calculate ASDAS. Subjects who have attained inactive disease status (defined as ASDAS < 1.3) at both Months 7 and 10 of open-label treatment are eligible to enter the double-blind withdrawal period (see Section 7.1.5.4 for more details); only these subjects are to be scheduled for the next clinic visit (Visit 24), which begins Period 2. Eligible subjects undergo stratified randomization in a 1:1:1 ratio to one of the following 3 treatment arms: 1) treatment-withdrawal (i.e., monthly injections of matching-placebo for golimumab), 2) golimumab QM (i.e., a full-treatment regimen, per approved labeling), or 3) golimumab Q2M (i.e., a reduced-treatment regimen, via monthly injections that alternate between golimumab and matching-placebo for golimumab). Strata are defined by the presence or absence of elevated CRP (> 6.0 mg/L vs. ≤ 6.0 mg/L) at the Screening visit. Eligible subjects receive their initial dose of blinded trial medication during Visit 24. Subjects who do not have inactive disease at Visit 23 do not enter Period 2; these subjects are discontinued from the study (and will have a safety follow-up telephone call 3 months after their last dose of trial medication).

Over the course of 12 months during Period 2, subjects return to the trial site for evaluation, including laboratory testing, approximately every 2 months (starting from the initial dose of double-blind trial medication). Subjects also continue to complete the BASDAI questionnaire twice monthly in order to rate disease activity. If there is an increase of ≥ 2 (on the 0 to 10 NRS) in BASDAI score compared to Month 10 (Visit 23), the trial site calls the subject to initiate a full evaluation of whether a “flare” (indicative of increased disease activity) is occurring; assessments include information obtained over the phone and/or at an unscheduled visit. A “flare” is defined by ASDAS collected at 2 consecutive assessments that both show absolute score ≥ 2.1 and/or post-withdrawal increase (i.e., change from Visit 23) of ≥ 1.1 (see Section 7.1.5.5 for details on confirming a “flare”).

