If a “flare” occurs during Period 2, then subjects discontinue blinded therapy (placebo, golimumab QM, or golimumab Q2M) and begin re-treatment with open-label golimumab QM. There should be an interval of at least 10 days between the last dose of Period-2 double-blind therapy and the first dose of open-label golimumab after a “flare” is confirmed. Thereafter, it is expected that re-treatment with open-label golimumab continues monthly through the end of Period 2. A clinical response to re-treatment is defined as a BASDAI score improvement of ≥ 2 or $\geq 50\%$ improvement (measured relative to the mean of the 2 BASDAI scores that were collected at the 2 consecutive assessments that defined the “flare”) that occurs within 3 months of restarting open-label treatment. If a subject shows insufficient improvement after 3 months of restarting open-label treatment for a “flare”, the investigator may consider discontinuing this subject from the study (based on clinical judgment) and will ensure a safety follow-up telephone call 3 months after the last dose of trial medication. If the subject is determined to have experienced a first “flare” between Months 19 and 22, the subject then completes a course of re-treatment (i.e., 3 monthly open-label golimumab injections) and will have a safety follow-up telephone call 3 months after the last dose of open-label golimumab. Subjects who do not experience a “flare” during Period 2 are to complete the study at Month 22 and will have a safety follow-up telephone call 3 months after their last dose of blinded trial medication.

Approximately 300 subjects are expected to enter Period 1. Based on the response to golimumab observed in the recently completed GO-AHEAD trial (P07642) [1], approximately 114 subjects are expected to continue into Period 2, based on attaining inactive disease status (ASDAS < 1.3) at both Months 7 and 10 of open-label golimumab. If the number of subjects who attain inactive disease is fewer than expected, additional subjects may need to enter Period 1 in order to randomize approximately 114 subjects with inactive disease status in Period 2.

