4.2.3 Rationale for Endpoints

4.2.3.1 Efficacy Endpoints

Inactive disease status and a disease “flare” in this trial are defined using the ASDAS. The ASDAS was developed by ASAS as an index for disease activity measurement in axial SpA that includes subjective measures (rated by the subject) and objective measure (CRP) to create a well-balanced index [3]. This score combines 5 disease activity variables that have only partial overlap, resulting in one single score with better validity, enhanced discriminative capacity, and improved sensitivity to change as compared with single-item variables. Cutoffs to identify “disease activity states” and “response criteria” using the ASDAS were first identified in 2011 [4]. This trial will use the cutoffs defined by ASAS:

- Level of ASDAS to identify subjects with inactive disease: ASDAS < 1.3 ;
- Level of ASDAS to identify subjects with a “flare”: ASDAS ≥ 2.1 (which defines high disease activity) and/or a change in ASDAS by ≥ 1.1 (which is considered a clinically important change).

The BASDAI score, which combines 6 questions that are self-assessed by subjects, is used to define a clinical response in this trial, both to open-label treatment with golimumab and to re-treatment with open-label golimumab after a “flare”. Clinical response is defined as a BASDAI score improvement by ≥ 2 (on a 0 to 10 scale) and/or score improvement by $\geq 50\%$. This definition of a “responder” is from the ASAS recommendations for use of TNF inhibitors in subjects with Axial SpA [2]. To assess the response to open-label golimumab, the response is compared with the BASDAI score at Month 0; to assess the response to re-treatment, the response is compared with the mean of the 2 BASDAI scores obtained when the “flare” was diagnosed.

To characterize the symptoms and signs of nr-axSpA in subjects treated with golimumab or withdrawn from golimumab, other secondary endpoints will be assessed in this trial. These include ASAS20, ASAS40, BASDAI50, and ASAS Partial Remission. All of these endpoints have been studied in many previous studies of axial SpA. Of note, in the GO-AHEAD

(P07642) trial in subjects with nr-axSpA, golimumab was shown to be superior to placebo for each of these endpoints [1].

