- b. Remote completion of the BASDAI questionnaire by subjects, twice monthly, using an electronic device.
- c. If the subject discontinued from the trial during Period 2, trial medication will not be administered at the DC clinic visit.
- d. If subjects report an increase of ≥ 2 BASDAI score compared with Month 10 (Visit 23), site is to call subject to obtain Patient Global Disease Assessment, and then use the CRP value from the previous clinic visit to calculate ASDAS. See Section 7.1.5.4 for more details.
- e. If “flare” (defined as ASDAS absolute score ≥ 2.1 and/or post-withdrawal increase (i.e., change from Visit 23) of ≥ 1.1 at 2 consecutive visits) is confirmed *during* a “flare confirmation” visit (based on the BASDAI and PGD_N obtained at that visit), subject will begin re-treatment with open-label golimumab for the confirmed “flare” at that visit. Clinic visits are then to be scheduled every 2 months from the date of the initial re-treatment with open-label golimumab
- f. If “flare” is confirmed *after* a “flare confirmation” visit (based on the CRP result as eventually received from that visit), then the subject is asked to return to the clinic to begin re-treatment with open-label golimumab for the “flare”. Clinic visits are then to be scheduled every 2 months from the initial re-treatment with open-label golimumab.
- g. The safety follow-up phone call is made approximately 3 months after the last dose of trial medication.
- h. When it is confirmed at Visit 23 that a subject is eligible for Period 2, site to call IVRS/IWRS to randomize the subject into Period 2 (Double-blind) prior to administering the trial medication; assign trial medication at all clinic visits; update the subject status at V48/DC visit.
- i. During Period 2, site personnel will administer the trial medication (± 5 days) during clinic visits. If subjects are self-injecting, the monthly dose to be administered (± 5 days) between clinic visits will be dispensed for subjects to self-inject at home.
- j. PEs would include a full skin assessment and would be directed to evaluate signs and symptoms of potential AEs assessment.
- k. If local law requires more frequent pregnancy testing, the site will perform the assessments as per local requirement
- l. At all visits, samples MUST be collected BEFORE the administration of trial medication.
- m. The same sample will be used for detection of antibodies to golimumab and neutralizing antibody analysis.

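### Section 8.6.1 scores re-treatment failure after discontinuation by inactive disease (ASDAS <1.3), although clinical response is defined by BASDAI, so an observed responder can be counted as a non-responder

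*Combined protocol and SAP*

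**What the plan says.** **Definition of response.** Section 2.1 states: "A clinical response to re-treatment is defined as a BASDAI score improvement of" at least 2 points or at least 50%, "that occurs within 3 months of restarting open-label treatment". Section 4.2.3.1 confirms BASDAI as the instrument and gives the reference value: "to assess the response to re-treatment, the response is compared with the mean of the 2 BASDAI scores obtained when the" flare was diagnosed. Neither section requires any ASDAS level for response to re-treatment.

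**Inactive disease is a different state.** It is defined as ASDAS <1.3 in Sections 2.1 and 4.2.3.1. Section 8.4.1.2 lists it as a separate secondary endpoint: "Proportion of subjects achieving inactive disease status".

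**Discontinuation rule.** Under missing data for the re-treatment response endpoint, Section 8.6.1 says that subjects who flare in Period 2 but "do not undergo re-treatment or discontinue prior to re-attainment of inactive disease will be counted in the group having" a flare without clinical response to re-treatment. The bullet sets no time limit and makes no exception for a subject whose BASDAI response has already been recorded.

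**Table 5.** The cell for this endpoint imputes non-response for early discontinuations, or for a flare without re-treatment. It does not mention inactive disease and does not define early. The footnote describes multiple imputation of the ASDAS components used to determine inactive disease, and the same footnote is attached to this BASDAI row.

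**The concern.** The endpoint and its discontinuation rule use different criteria. The matching bullet for the primary endpoint, in the same section, is keyed to that endpoint's own event: leaving before a flare counts as a flare. The parallel rule here would refer to leaving before clinical response. It refers to an ASDAS state instead.

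Two subjects with the same BASDAI course can therefore be scored differently because one of them left later. Response is judged within 3 months but the rule is open-ended. A subject who responds at month 1 and leaves several months later, without having reached ASDAS <1.3, is literally a failure on an outcome that was already settled. Section 8.6.1 also analyses time to clinical response in the same flare analysis set. That subject would have a dated response in that analysis and be a non-responder in the proportion.

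At stake is the first-listed secondary objective: how often a flare after withdrawal or dose reduction is recaptured. Section 4.3 names poorer response on restarting golimumab as a risk of the treatment paradigm, so this estimate will be read closely.

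**Working it through.** The plan states no response rate, precision or power for this endpoint, so it has no figure of its own to reproduce. The enrolment arithmetic behind the denominators does reproduce: 300 × 0.38 = 114, and 114 / 3 = 38 per arm (Section 8.9).

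**1. Does BASDAI response imply inactive disease?**

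Inputs:
- BASDAI = 0.2 × (Q1 + Q2 + Q3 + Q4 + 0.5 × [Q5 + Q6]) (Section 8.4.3.1).
- ASDAS = 0.12 × Q2 + 0.06 × Q6 + 0.11 × patient global + 0.07 × Q3 + 0.58 × ln(CRP + 1) (Section 8.4.3.2).
- At low CRP, "a value of 2 mg/L is used to calculate the ASDAS" (Section 8.4.3.2).

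Illustrative assumption: all items, including patient global, equal a common value x; CRP is at the floor; both flare assessments are the same. Then BASDAI = x and ASDAS = 0.36x + 0.58 × ln 3 = 0.36x + 0.637. Starting from x = 6, ASDAS is 2.80, a flare on the absolute criterion.

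| Items | BASDAI change | BASDAI response? | ASDAS after | Inactive? |
|---|---|---|---|---|
| 6 to 4 | −2.0 (33%) | yes | 2.08 | no |
| 6 to 3 | −3.0 (50%) | yes | 1.72 | no |
| 6 to 2 | −4.0 (67%) | yes | 1.36 | no |

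ASDAS <1.3 needs x < (1.3 − 0.637) / 0.36 = 1.84. At CRP 10 mg/L it cannot be reached even with every item at 0, because 0.58 × ln 11 = 1.39. Unremarkable BASDAI responders therefore fail the criterion used in the discontinuation rule.

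**2. Can the reverse happen?**

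Yes, because ASDAS omits Q1, Q4 and Q5. Hold those three at 5. Let Q2, Q3, Q6 and patient global fall from 4 to 1, and CRP from 3 to 2 mg/L.
- BASDAI before: 0.2 × (5 + 4 + 4 + 5 + 0.5 × 9) = 4.5. After: 0.2 × (5 + 1 + 1 + 5 + 0.5 × 6) = 3.0. The change is 1.5 points (33%), so there is no response.
- ASDAS before: 0.36 × 4 + 0.58 × ln 4 = 2.24. After: 0.36 + 0.637 = 1.00, so the subject is inactive.

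If this subject then discontinues within 3 months, the Section 8.6.1 bullet does not impute non-response, although no BASDAI response occurred.

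**3. What does one misclassified subject cost?**

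The flare analysis set is the placebo and every-2-months subjects who flare (Section 8.5.1). Placebo flare is taken as 60–80%, from the 20–40% flare-free rows of Table 7. The flare rate on the every-2-months regimen is assumed to be 20–40%, since Section 8.9 says it is not known. All flares are treated as observed.
- Low: 38 × 0.60 + 38 × 0.20 = 30.4, so one subject is 1/30.4 = 3.3 points.
- High: 38 × 0.80 + 38 × 0.40 = 45.6, so one subject is 1/45.6 = 2.2 points.

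For scale, the planned Clopper-Pearson 95% intervals at assumed response rates of about 50% and 90% are:

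| Responders / N | Rate | 95% CI | Half-width |
|---|---|---|---|
| 15/30 | 50.0% | 31.3–68.7 | 18.7 |
| 27/30 | 90.0% | 73.5–97.9 | 12.2 |
| 23/46 | 50.0% | 34.9–65.1 | 15.1 |
| 41/46 | 89.1% | 76.4–96.4 | 10.0 |

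**The case against.** The best defence is the heading. The bullet sits under missing data, and a BASDAI response already on file is not missing. Table 5 restates the rule without inactive disease, so the intent may have been to impute only undetermined outcomes. That may well be so, but the text does not limit itself in that way. It says such subjects will be counted as non-responders, and Table 5's early discontinuations are undefined and exempt nobody. Section 8.6.1 defers only the imputation procedure to the supplemental SAP; the discontinuation rule is given as complete. A programmer following it would override observed data.

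The second defence is that the affected group is narrow: flared, re-treated, BASDAI responder, not at ASDAS <1.3, then discontinued. Section 2.1 names insufficient improvement after 3 months as a reason the investigator may consider discontinuation, and subjects who leave without a BASDAI response fail under either wording. This stands, and it limits the size of the problem.

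Two stronger readings are tempting and are not supported:
- A reader might infer that the rule can only lower the recapture rate. The reverse case in the working shows otherwise: there the rule leaves a BASDAI non-responder without imputed failure, and the plan does not say how that subject is then scored. Understatement is the main direction, not the only one.
- A reader might infer that a responder who leaves early has no CRP and so could never be shown to be inactive. Section 7.1.4.1 asks for the discontinuation-visit activities to be performed on leaving, and the Section 6.2 flow chart includes CRP, patient global and BASDAI at that visit. Section 8.6.1 also provides multiple imputation for missing components, CRP among them.

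**Conclusion.** The rule is wrong as written, for a secondary descriptive endpoint. It judges a BASDAI outcome by an ASDAS state and, read literally, scores an observed responder as a failure. Its main effect is to understate recapture.

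The documents give neither a discontinuation rate nor a response rate after re-treatment, so the number affected cannot be computed and none is assumed. Each affected subject moves the estimate by about 2 to 3 percentage points under the assumed flare rates. That is small against a confidence-interval half-width of about 10 to 19 points. It is nevertheless an error of definition, which a larger sample would not remove.

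A reader should not infer any effect on the main conclusion. The primary endpoint has its own rule, Section 8.1 names no key secondary endpoints, and Section 8.8 treats all other efficacy analyses as supportive or exploratory.

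**What to change.** Three wording changes, with no change to data collection or to the conduct of the trial:

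1. In the Section 8.6.1 discontinuation bullet for re-treatment response, replace the condition on regaining inactive disease with *attainment of clinical response as defined in Section 2.1*.
2. In the Table 5 cell for this endpoint, change only the reference to early discontinuations, to *discontinuations before attaining clinical response*. Keep the clause on a flare without re-treatment and the multiple-imputation clause.
3. For this row, in the Table 5 footnote and the supplemental SAP, state that the imputed components are the BASDAI items Q1–Q6. The ASDAS components now named omit Q1, Q4 and Q5, which the BASDAI score needs.

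The cost is one phrase, one table cell and one footnote. Section 8.0 already allows changes to analyses before unblinding to be documented in the supplemental SAP, and making this one then avoids any appearance of a post hoc choice.
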